1.2 Feasibility Questions

- Can sufficient numbers of patients with AF be identified and recruited onto a study to investigate the impact of bleeding events, related to anticoagulant use, on quality of life?
- Can quality of life impact be measured for patients who are prescribed anticoagulants and experience bleeding as a side effect?

We hypothesise that there is a considerable and sustained impact on AF patient's quality of life (QoL) when they experience a bleed while anticoagulated, whether that bleed is major or minor in severity. Understanding the nature and extent of this impact on patients' QoL is expected to guide physicians' risk assessment when seeking to effectively anticoagulate patients with AF.

2 OBJECTIVES

2.1 Primary Objectives

To test the feasibility of i) identifying and recruiting patients with both minor and major bleeds³² as a result of anticoagulant treatment for AF associated events, and ii) measuring their QoL in both primary and secondary care settings.

2.2 Secondary Objectives

- To describe and interpret the observed differences in QoL by type of bleed.
- To describe the treatment received and the nature of the bleed experienced by the patient.
- To undertake structured qualitative interviews to gain detailed insight into issues from a patient perspective, for those who live with AF and have experienced a recent bleed while taking anticoagulants.
- To observe appropriateness of three chosen PROMs (EQ5D, AFEQT and PACT-Q, part 2) in capturing QoL data, specifically post a bleeding event for AF patients who are taking anticoagulants.

3 STUDY DESIGN

3.1 Overview of Study Design

A descriptive evaluation of the QoL of patients with AF experiencing a bleed, both in primary care and secondary care settings (hospital wards and the emergency department (ED)).

Patient Recruitment & Study Sites

All patients will be targeted based on strict inclusion and exclusion criteria, as detailed further below (Section 3.2.1 & 3.2.2). Recruitment strategies will vary considerably in order to limit unconscious recruitment bias (for example, taking care not to direct all efforts only towards those patients who are more disposed to seek medical care when experiencing bleeds). Initially, eligible patients will be identified from regular searches in secure databases in both primary (GP surgeries) and secondary care

(ward/emergency department [ED]). JCRF staff will provide recruitment support by regular screening of A&E databases at Morriston hospital. Letters of invite will be sent out to patients who appear eligible via secondary care. NO on-site visits will take place by JCRF staff due to restrictions surrounding COVID-19 and social distancing. Patients will be subsequently approached about the study by means of a face-to-face referral in clinics where viable, in line with current consultation arrangements during the COVID-19 period, or, alternatively, study information will be posted to capture patients with AF who may not have recently visited clinics, wards, or emergency department (ED). Where appropriate, study posters will be placed in optimal locations such as general practice (GP) clinics to display information about the study, in lay terms, to encourage discussion with GPs concerning all recent minor bleeds (as defined by ISTH32), which the patient may not have thought relevant enough to mention otherwise. Leaflets and study cards will be provided, which will allow potential participants to take away study information for consideration, including by friends and family members. Patients interested in participating in the study will be instructed to contact the clinical research team directly to streamline screening and enrolment process, and to limit time burdens on healthcare staff.

Based on data provided by anticoagulation clinics within the Swansea City Health Cluster (eight general practices in the Swansea area), it is estimated that there are approximately 500 patients with AF who are currently taking prescribed anticoagulants. All eligible patients identified within the Health Cluster, will be contacted via post and, if willing, asked to report on any bleeds within the recruitment period. A further recruitment drive will take place synchronously in hospital settings, where all patients who attend the emergency department (ED) of Morriston Hospital or admitted to the wards due to bleeds, will be approached for participation in the study. These patients will be identified following admission, but existing in-patients at study outset will be approached if it is appropriate to do so. Lastly, e-cards will be sent to specific patient groups as required, on forums, social media, web site and newsletters run by online AF support networks. Finally, patients will be informed of the study via online AF support groups on forums, social media pages and from a large database of patients, managed by the support group. Approximately 60,000 patients are held on the database in total, which will be accessed and filtered to identify eligible AF patients. Consent will be received digitally and an online link to the questionnaires will be sent to those who wish to participate. Follow-up data collection for these patients will also be conducted digitally.

Recruitment is anticipated to commence in September 2020 and will continue for 6 months – a key decision made in light of the COVID-19 outbreak. Although the study will aim to recruit between 50 and

80 patients in the first instance, all suitable patients who are willing to partake in the study will be included. A maximum of 200 patients will be permitted to enroll if successfully screened.

The research team will not have any contact with the patient unless the patient registers their interest in the study or if they reply following invitation from the healthcare provider.

Screening & Enrolment

The study will aim to enroll all patients who have AF and are anticoagulated, and who have experienced a bleed within a maximum of 30 days at point of enrolment. Patients experiencing bleeds over 30 days prior to enrolment will not be considered for the study at this stage. Numbers of minor and major bleeds reported will be monitored to ensure equal numbers of patients experiencing both types of bleeds are included, as far as feasible. Should an unequal proportion of n numbers occur between type of bleed, patients will not be turned away if they are willing to participate. Researchers will monitor numbers closely and attempt to achieve an equal proportion of minor and major bleed patients. If a balance of major and minor bleeds cannot be achieved within the chosen study population, it will be noted for informing study design of any related future studies.

Patients who meet all study criteria will undertake an informed consent process, where they will be provided with full study details in a patient information sheet (PIS) and asked to sign appropriate documentation to indicate agreement to take part. Patients will have at least 24 hours to deliberate if needed and will have the opportunity to ask any questions before consenting to take part. For surveys which are completed online via a survey link, e-consent will be received according to HRA advice. Patients must agree to provide current contact details for the study team to be kept confidentially by the study team for follow-up purposes. Basic patient demographic information will be collected by qualified research nurses and recorded on case report forms (CRFs), along with details of any bleed(s) experienced. Additional anecdotal questions will be asked relating to ongoing patient management of atrial fibrillation during the current pandemic of Coronavirus, such as the ease of seeking medical care in a situation of a lockdown and social distancing where visits to anticoagulation clinics are limited or entirely stopped. All study documentation will comply with Good Clinical Practice (GCP) guidelines and General Data Protection Regulation (GDPR).

Patient Questionnaires

All patients will be asked to complete three questionnaires for the study: EQ-5D-5L, Perception of Anticoagulant Treatment Questionnaire, **Part 2 only** (PACT-Q, Part 2) and Atrial Fibrillation Effect on QualiTy-of-life (AFEQT), which should take no longer than 30 minutes in total to complete^{23, 39}. Considerations have been made, as far as possible, to minimize impact on patient's time. Questionnaires will be conducted at two time-points for this study; an initial round will be completed at point of consent/enrolment and a second identical set of questionnaires at 90±14 days post-enrolment. Patients will complete the initial round of questionnaires immediately after consent process, to ensure that loss to follow-up is controlled. An option to take part in a further qualitative interview, after the 90-day follow up, will be included in both questionnaire sets. Initial questionnaires will be provided electronically via tablet devices or on paper copies, if patients prefer. Follow-up questionnaires will be sent out either through the post 3 weeks prior to the 90-day follow-up date, along with a stamped addressed envelope for ease of return or enrolled patients who prefer to complete data collection electronically will be sent a survey link. Patients will be asked in an accompanying letter to complete and return the questionnaires within the 90±14 day time-frame. If no reply is received within 2 weeks of first correspondence, a reminder letter along with a second copy of all questionnaires will be delivered. The PROMs for the study have been carefully selected based upon study requirements and desired outcomes as far as possible, in lieu of having access to a validated bleed-specific QoL questionnaire. Data collected using the chosen questionnaires will also allow comparable analysis with more substantial databases, as data will line up with previously collected QoL data in AF patients, where identical questionnaires have been widely used.

Patient Interviews

To capture valuable, emotive data in the form of patient thoughts and feelings in relation to the study objectives, a small subset of patients will complete short, structured interviews, which will be conducted by research staff at Swansea Trials Unit. It is anticipated that 10 interviews will be sufficient to identify key themes from patients. Interviews will stop if saturation is reached before then and no new themes are identified; interviewees will be randomly selected from all patients who have indicated that they would be willing to take part. Any patient who has consented to be interviewed *and* completed initial questionnaires as a minimum, will be contacted (i.e. patients who fail to complete a second set of questionnaires at 90±14 days can still take part in study interviews, if contacted successfully). However, patient interviews will only take place after the 90-day follow-up point post-enrolment. Interview

questions will be designed in close collaboration with the study's consultant haematologist to ensure that appropriate questions are asked in a concise and respectful way. Patients will be asked to expand more specifically on bleeding events and consequent level of impact on quality of life **at time of event (bleed)** in comparison to the effect **3 months (90 days) later**. Additionally, patients will be asked to give opinions on the chosen study PROMs on relevance to the true burden of AF and if the questionnaires have overlooked any important quality of life concerns for patients with AF. Recall bias will be managed as far as conceivable by ensuring that interviewers are sufficiently experienced in conducting interviews efficiently and interview questions are impartial. Any information given by patients during an interview will be verified where possible.

All interviews will be recorded upon patient consent and transcribed at a later date. Interview questions will be identical across all patients.

Data Handling & Storage

Paper copies of CRFs and questionnaires will be transcribed into the study database, where the data will be checked for consistency and accuracy, alongside other data collected electronically.

Data will be hosted securely on the REDCap data management system (licensed to Swansea Trials Unit (STU)). Study data will be held anonymously within REDCap and any identifying data (including protected characteristics) will be kept separately, secured by access restrictions.

Data Analysis and Reporting

Descriptive analysis of QoL reported by AF patients following a minor or major bleed while anticoagulated. Comparison to age-adjusted population norms may be insightful but no comparisons with controls are planned for this feasibility assessment.

A brief thematic analysis (Braun and Clarke, 2006³³) will be conducted on transcribed interview data, to draw out important common themes relating to the study question, which will not be directly captured through the chosen PROMs. Specific qualitative data analysis software, NVivo 12, will be used for additional insight and to identifying trends in unstructured data captured during study interviews.

A final report will be submitted to the funder, BMS, in month 18 of the study. Alongside this, publications in the form of at least one conference presentations and one peer-review publication will be prepared and submitted between months 16 and 20.

[figure not shown]
*Project timescales*Start date: **01st January 2020**First Patient First Visit (anticipated): **01st September 2020**End date: **01st September 2021**

Duration: 20 months (16 months data collection, analysis and study report, 4 months peer review publication and dissemination)

EQUAL-AF Project timescales- Phase 1 feasibility study

TASK	Months																			
	1	2	3	4	5	6	7	8	9	10	11	12	13	14	15	16	17	18	19	20
Work Package 1																				
Identify appropriate PROMs, arrange licenses for PROM use, finalise protocol, completion of IRAS application for Ethics and R&D approvals	■	■	■	■	■	■	■	■												
RedCap database development, production of tablet and app versions of questionnaires, CRF design					■	■	■	■												
Site set up -Primary care, ED and ward (delay due to COVID-19)								■	■	■										
Work Package 2																				
Patient recruitment (delayed in light of COVID-19 outbreak)									■	■	■	■	■							
Work Package 3																				
Database cleaning and locking														■	■	■				
Data analysis															■	■				
Final report to BMS																■				
Publications, peer review reporting and dissemination																	■	■	■	■

Study Flowchart

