- A sub-set of 10 patients will be asked to take part in a qualitative semi-structured interview, which will aim to further describe patient QoL after a bleed, while anticoagulated. Patients completing the interview will also be asked to provide any comments and opinions regarding the suitability of the chosen study PROMs for properly capturing all QoL issues after a diagnosis of AF.

Study Population:

Primary and secondary care patients with AF (aged ≥ 18) who are actively prescribed oral anticoagulant therapies (OATs) and have recently experienced bleeds, up to a maximum of 4 weeks prior to enrolment. No upper age limit will apply but potential study participants must match all inclusion/exclusion criteria, detailed fully in section 3.2.1 & 3.2.2.

Data Collection Methods:

Data sources: Electronic and/or paper records kept at primary and secondary care will be regularly searched for identification of suitable patients. Patients routinely attending anticoagulation clinics will be asked if they have experienced a recent bleed, and those who present as eligible will be asked to take part in the study. Posters placed in appropriate locations in GP clinics will encourage patients who have AF and are anti-coagulated to discuss minor bleeds with GPs. Lastly, e-cards will be sent out to patients with AF groups on forums, social media pages, web site and newsletters run by online AF support networks.

Exposure: Anticoagulated to prevent stroke following diagnosis of AF.

Data collection: Data will be obtained using questionnaires supplied on paper case report forms or via an electronic device, depending on participants' preference and up to date restrictions due to coronavirus outbreak in regards to using touchscreen devices. Data captured via an electronic device will be submitted directly to a REDCap database which has been designed for the study. Completed paper versions of the survey will later be transcribed into the database by a member of the study team. A random subset of enrolled AF patients will also undergo recorded interviews with research nurses in order to capture valuable free-form, emotive data regarding effect on quality of life after a bleed and to document patient opinion on current available PROMs used in the study.

Data Analyses:

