Descriptive analysis of QoL reported by AF patients following a minor or major bleed while anticoagulated. Comparison to age-adjusted population norms may be insightful but no comparisons with controls are planned for this feasibility assessment, as no control patients will be enrolled.

Sample Size/Power:

Between 50 and 80 patients are expected¹, stratified into major and minor bleeds². Depending on recruitment efficacy, a maximum of 200 patients will be enrolled.

Limitations/Strengths:

The main limitation of the study is the lack of access to a suitable PROM, which specifically captures the true impact of bleeding on quality of life (QoL). The study will instead utilise previously validated generic and disease specific health-related quality of life (HRQoL) measures and compare them with population norms.

As this is a feasibility study it is unknown how successful chosen recruitment strategies will be for the study in the study sites and populations selected.

This study will enhance currently limited research into how bleeding specifically affects QoL in patients diagnosed with AF.

TABLE OF CONTENTS

TITLE PAGE 1

DOCUMENT HISTORY	3
RESEARCH REFERENCE NUMBERS	3
COVID-19 IMPACT STATEMENT	5
SYNOPSIS 6	
TABLE OF CONTENTS.....	9
1 INTRODUCTION.....	10
1.1 Study Rationale	10
1.2 Feasibility Questions.....	11
2 OBJECTIVES	12
2.1 Primary Objectives.....	12
2.2 Secondary Objectives	12
3 STUDY DESIGN	12
3.1 Overview of Study Design.....	12
3.2 Study Population.....	20
3.2.1 Inclusion Criteria	20
3.2.2 Exclusion Criteria	20
3.3 Data Source/Data Collection Process	21
3.3.1 Patient Reported Outcome (PRO) Measures	22
3.4 Definitions of Study Variables	23
3.4.1 Outcomes/Endpoint Variables	25
4 STATISTICAL ANALYSIS.....	25
4.1 Progression Criteria	26
5 STUDY LIMITATIONS/STRENGTHS	26
6 STUDY CONDUCT	27
6.1 Ethics Committee Review and Informed Consent.....	27
6.1.1 Ethics Committee Review	27
6.1.2 Informed Consent	27
6.2 Responsibilities within the Study.....	27
6.2.1 Sponsor Roles and Responsibilities	27
6.2.2 Principal Investigator Roles and Responsibilities	28
6.2.3 Steering Committee	28
6.3 Confidentiality of Study Data.....	28
6.4 Quality Control.....	29
6.5 Database Retention and Archiving of Study Documents	29
6.6 Registration of Study on Public Website	29
7 ADVERSE EVENT REPORTING	29
8 LIST OF ABBREVIATIONS	30
9 SCIENTIFIC PUBLICATIONS	31
10 REFERENCES.....	32

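### Interviewees are drawn without regard to bleed type, so if major bleeds are rare among willing patients, few or none may be interviewed and saturation may be declared too soon

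*Protocol*

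**What the plan says.** On the number of interviews, Protocol section 3.1 (Patient Interviews) states: "It is anticipated that 10 interviews will be sufficient to identify key themes from patients". The stopping rule is: "Interviews will stop if saturation is reached before then and no new themes are identified". The selection rule is: "interviewees will be randomly selected from all patients who have indicated that they would be willing to take part". The Synopsis (Data Collection Methods) agrees: "A random subset of enrolled AF patients will also undergo recorded interviews with research nurses". No section sets a quota by bleed type, a minimum number of interviews, or saturation within each type.

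On the mix of bleeds among enrolled patients, section 3.1 (Screening & Enrolment) says: "Researchers will monitor numbers closely and attempt to achieve an equal proportion of minor and major bleed patients". It also allows that this may fail: "Should an unequal proportion of n numbers occur between type of bleed, patients will not be turned away if they are willing to participate". The balance is a target for enrolment only. It does not carry over to the interviews.

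Section 3.4 counts every bleed that is not major as minor, with shaving cuts and bruising among the examples. The Synopsis (Secondary outcome measures) places the clinician's major/minor classification in data cleaning and analysis. Section 3.3 (Outcomes) and section 4 also describe it as done afterwards.

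**The concern.** The hypothesis in section 1.2 covers major and minor bleeds alike, and one secondary objective in section 2.2 is to describe how quality of life differs by type of bleed. The interviews ask patients how the bleed affected them at the time and 90 days later, and whether the questionnaires missed anything. With at most 10 interviewees drawn from one undivided pool, whether major-bleed patients are heard at all is left to chance.

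The stopping rule can add to this. If the first several interviewees all had minor bleeds and gave similar accounts, new themes could dry up and interviewing could end before a major-bleed patient is reached. The loss could be hard to make good after the interviews have closed.

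A low major share is plausible on the protocol's own terms. The minor category is very broad, posters invite patients to raise minor bleeds, and online networks are approached. On the other side, patients attending the emergency department or admitted to wards with bleeds are also approached, and that route is likely to bring in major bleeds. The document does not let one say which influence will dominate.

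**Working it through.** The figure of 10 interviews comes with no formula or numerical inputs, so there is nothing to reproduce. The check is how often an unstratified random draw would miss major-bleed patients.

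**Inputs from the protocol**
- Interviews: n = 10, or fewer at saturation (section 3.1, Patient Interviews).
- Enrolment: "Between 50 and 80 patients are expected" (Synopsis, Sample Size/Power), with a maximum of 200.
- Intended mix: equal numbers of major and minor bleeds, as far as can be achieved (section 3.1, Screening & Enrolment).

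**Assumptions (not in the protocol)**
- Willing pool: N = 50, with 80 and 20 as alternatives.
- Major share of that pool: 50%, 30%, 20% or 10%, giving M = 25, 15, 10 or 5 when N = 50.
- One draw from the whole pool, with everyone drawn interviewed.
- An early stop at n = 5, for illustration.

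**Formulas** (hypergeometric)
- P(no major) = C(N − M, n) / C(N, n)
- P(at most one major) = P(no major) + M × C(N − M, n − 1) / C(N, n)

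**Worked case, N = 50, M = 5, n = 10**
- P(no major) = (40 × 39 × 38 × 37 × 36) / (50 × 49 × 48 × 47 × 46) = 78,960,960 / 254,251,200 = 0.311.
- P(exactly one) = 5 × (10/36) × 0.3106 = 0.431, because C(45,9) / C(45,10) = 10/36.
- P(at most one) = 0.311 + 0.431 = 0.742.

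**Intended mix, N = 50, M = 25, n = 10**
- P(no major) = C(25,10) / C(50,10) = 3,268,760 / 10,272,278,170 = 0.0003.

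**Results for N = 50**

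| Major share | No major in 10 | At most one in 10 | No major if stopped at 5 |
|---|---|---|---|
| 50% | 0.03% | 0.5% | 2.5% |
| 30% | 1.8% | 12% | 15% |
| 20% | 8% | 35% | 31% |
| 10% | 31% | 74% | 58% |

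**Sensitivity to pool size, n = 10.** With N = 80 the chance of no major is 0.05%, 2.2%, 9.2% and 32.6% at the four shares. With N = 20 it is 4.3% at a 20% share and 23.7% at 10%. The major share drives the result much more than the pool size does. If major-bleed patients volunteer less often, their share of the willing pool falls below their share of enrolment, and the lower rows apply.

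The at-most-one column matters more than the no-major column, since a single interviewee can hardly support themes for a bleed type.

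**The case against.** Four points can be made for the plan, and each has some force.

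1. The protocol aims for equal numbers. If that is achieved, 10 random interviews will almost never miss major bleeds (0.03%), and at a 30% share the chance is still only 1.8%. This stands. A reader might infer from the lower rows of the table that major-bleed patients will probably be missing. The documents do not support that, because they give no expected major share.

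2. A reader might infer that feedback on the questionnaires would describe minor bleeds only. That is not so. Section 4 provides for open-ended written feedback on each questionnaire from eligible patients on the CRFs and survey links, whoever is interviewed. This partly protects the objective on questionnaire suitability. It does not replace the fuller interview account of what a major bleed was like.

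3. The interview objective in section 2.2 asks only for patients with a recent bleed, and the planned thematic analysis looks for common themes. The contrast by bleed type is a separate objective that questionnaire data from all patients can serve. So this is a sampling weakness, not an internal contradiction.

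4. A reader might infer that early saturation would be false. That is not established: it would require few or no major-bleed interviewees and also themes that differ by type. Saturation is a judgement, and nothing stops the analysts from weighing bleed type. The supportable statement is that it may be premature.

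An unstratified draw also reflects the recruited patients and fits the stated wish to limit bias. A draw at random within type keeps selection random but gives up that reflection of the mix.

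**Conclusion.** The point holds as a conditional weakness. Under the written rules, coverage of major bleeds in the interviews depends on the major share of the willing pool, which the protocol neither states nor controls. At the intended equal mix the risk is negligible. It becomes material at a share of about 20% or less: with 50 willing patients and 10 interviews, the chance of no major-bleed interviewee is 8% at a 20% share and 31% at 10%, and of at most one 35% and 74%. An early saturation stop raises the chance of none.

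These figures rest on assumed shares, an assumed pool and a single draw. No progression criterion in section 4.1 (recruitment, retention, questionnaire completion) is touched. This is a cheap improvement to a stated rule, not an error that undermines the study.

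**What to change.** In section 3.1 (Patient Interviews), with the Synopsis brought into line, replace the single draw with a random draw within bleed type. One workable form is 5 major and 5 minor; if fewer than 5 major-bleed patients are willing, take all of them and fill the remaining places with minor-bleed patients. Add that interviewing does not stop for saturation until the available major-bleed interviewees have been heard. The split of 5 and 5 is an example; no figure in the protocol determines it.

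Selection stays random, and the chance of selecting no major-bleed patient falls to zero whenever at least one is willing and can be contacted.

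The costs are modest:
- A provisional clinician classification is needed before interviewees are drawn. Interviews take place only after the 90-day follow-up point, and section 3.1 (Screening & Enrolment) already calls for running counts by type, so the added work is small. The text on later classification in the Synopsis, section 3.3 (Outcomes) and section 4 must be aligned.
- The interview set will no longer mirror the enrolled mix. The report should say so and should identify which themes came from which bleed type.

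### The 16-month span for data collection, lock, analysis and funder report ends before the last 90±14-day follow-up window closes, and the protocol gives two recruitment lengths and two report months

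*Protocol*

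**What the plan says.** All the timing statements are in Protocol section 3.1.

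- **Project timescales, dates.** Start 1 January 2020, anticipated first patient visit 1 September 2020, end 1 September 2021. The split is "Duration: 20 months (16 months data collection, analysis and study report, 4 months peer review publication and dissemination".
- **Project timescales, timetable.** Recruitment is marked in months 9 to 13. The row "Database cleaning and locking" is marked in months 14 to 16, data analysis in 15 and 16, the funder report in 16, and publication in 17 to 20. No row covers the 90-day follow-up or the interviews.
- **Patient Recruitment & Study Sites.** "Recruitment is anticipated to commence in September 2020 and will continue for 6 months".
- **Patient Questionnaires.** After the enrolment set there is "a second identical set of questionnaires at 90±14 days post-enrolment". For the postal route, "Follow-up questionnaires will be sent out either through the post 3 weeks prior to the 90-day follow-up date".
- **Patient Interviews.** These take place only once the 90-day point has passed.
- **Data Analysis and Reporting.** "A final report will be submitted to the funder, BMS, in month 18 of the study".

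Section 4.1 then makes retention of at least 50% of enrolled patients, and 40% PROM completion at follow-up, criteria for progression.

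**The concern.** The duration line and timetable leave no room for follow-up of the last patients enrolled. Cleaning and locking start in the month after the last marked recruitment month, although each patient's second questionnaire set is not due until about three months after enrolment. The text and timetable also differ on how long recruitment lasts and when the funder report is due, so a reader cannot tell which schedule governs.

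Two of the progression criteria in section 4.1 are assessed at this follow-up. A lock and report on the stated month-16 schedule would be made before some patients had had their full window to respond.

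**Working it through.** **Inputs.** Month 1 is January 2020 and first enrolment is 1 September 2020 (Project timescales). Recruitment is five months (timetable) or six (text). The window is 90 − 14 = day 76 to 90 + 14 = day 104 (Patient Questionnaires).

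**The plan's own figure.** 1 January 2020 plus 20 months is 1 September 2021, so the stated total reproduces. The 16 + 4 split matches the timetable: report in month 16, publication in months 17 to 20. Month 16 ends on 30 April 2021.

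**Last patient's dates.** Each is last enrolment plus the stated number of days.

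| | Five months (timetable) | Six months (text) |
|---|---|---|
| Last enrolment | 31 Jan 2021 | 28 Feb 2021 |
| Window opens (+76) | 17 Apr 2021 | 15 May 2021 |
| Day 90 | 1 May 2021 | 29 May 2021 |
| Window closes (+104) | 15 May 2021 (month 17) | 12 Jun 2021 (month 18) |
| Close minus 30 Apr | 15 days | 43 days |

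On six months the last patient's whole window lies after month 16. If that patient uses the postal route, the questionnaire is due out at 90 − 21 = day 69, which is 8 May 2021, also after month 16. For every window to close by 30 April 2021, the last enrolment would have to be 30 April − 104 days = 16 January 2021, earlier than either recruitment length allows.

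**Share of patients affected if the database were locked on 30 April 2021.** With uniform accrual (an assumption), the share is the number of enrolment days after the latest enrolment date that still reaches the given day, divided by the length of recruitment. That latest date is 16 January 2021 for day 104 and 13 February 2021 for day 76.

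- Five months (153 days): window incomplete 15/153 = 9.8%; window not yet open 0/153 = 0%.
- Six months (181 days): window incomplete 43/181 = 23.8%; window not yet open 15/181 = 8.3%.

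**Month-18 report.** Month 18 ends on 30 June 2021. From 12 June that leaves 18 days for lock, analysis and report; from 15 May it leaves 46. Nobody is cut off, but on six months the time is short.

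**Alternative reading of the 16 months.** Counted from the first patient visit, they would end on 31 December 2021, after the stated end date. That reading fails.

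**Room before 1 September 2021.** From 15 May there are 109 days; from 12 June there are 81. The timetable gives months 14 to 16 to lock, analysis and report, which is 28 + 31 + 30 = 89 days. Kept in full after the last window, this leaves 109 − 89 = 20 days on five months and 81 − 89 = −8 days on six.

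**The case against.** The best defence is that neither schedule does much harm when read by itself. On the timetable alone the overrun is 15 days, on a chart drawn in whole months with an anticipated first-patient date; every patient's window has opened by 30 April, and only the last day's enrollees (1/153, under 1%) are short of day 90. On the text alone, six months of recruitment and a month-18 report cut nobody off. The 24% and 8% shares arise only when the text's recruitment length is paired with the month-16 finish. This stands, and the figures should be read that way. It does not remove the contradiction, because both schedules are current text and the duration line fits neither recruitment length.

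Uniform accrual is also open to challenge. Posting invitations to all eligible patients in the Health Cluster could bring enrolment forward and shrink the shares. Site set-up marked through month 10 could push it back and enlarge them.

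A reader might go further and infer that an early lock must understate retention, perhaps pulling a passing result below 50%. The document does not support that. Section 4.1 lists retention separately from PROM completion and does not define it as questionnaire return. If it means not withdrawn or still contactable, patients not yet due could count as retained. The denominator for PROM completion is not stated either.

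Nor can it be said that no cut-off or counting rule exists. Such rules commonly sit in the statistical analysis plan, which is not at hand, and the study flowchart is not visible in the text reviewed.

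**Conclusion.** The point holds as an inconsistency in the schedule. The 16-month span cannot contain the planned follow-up on either recruitment length: the last window closes 15 days (five months) or 43 days (six months) after month 16 ends. These overruns are calendar arithmetic and need no accrual assumption. Section 3.1 also contradicts itself on recruitment length (six months against five) and on the report month (18 against 16).

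The consequence is conditional. Only if a month-16 lock were kept, and accrual were uniform, would about 10% or 24% of patients have an incomplete window, and about 0% or 8% no open window. Follow-up data behind the section 4.1 criteria could then be truncated. No direction or size is claimed for retention or PROM completion. The correction is worth making because section 6.2 requires the study to be run as the protocol describes.

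**What to change.** 1. State one recruitment length and one funder-report month, and use them in the recruitment text, the reporting text, the duration line and the timetable.
2. Place database lock after the last patient's day 104: after 15 May 2021 on five months of recruitment, or after 12 June 2021 on six. Put analysis and the funder report after the lock.
3. Add timetable rows for the 90-day follow-up and for the interviews, which cannot start before day 90 and still need transcription and thematic analysis.

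**Cost.** The progression criteria and outcomes are untouched. Under section 6.2 the revision needs authorisation by the sponsor and the funder. The funder report may come later, the 16 + 4 split changes, and publication time shrinks. If lock, analysis and report keep their full three months, five-month recruitment leaves about 20 days before the end date and six-month recruitment overruns it by about 8. That work must then be compressed or overlapped, or the end date restated.
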